4.2.9.2 Progression-free survival

PFS will be analysed using Kaplan-Meier (K-M) methodology from which the median and its 95% CI will be provided, together with event rates at clinically important landmarks (ie, at 6, 12, 18 and 24 months).

The treatment status at progression of patients at the time of analysis will be summarised. This will include the number (%) of patients who were on treatment at the time of progression, the number (%) of patients who discontinued study drug prior to progression, the number (%) of patients who have not progressed and were on treatment or discontinued treatment. This will also provide the distribution of the number of days prior to progression for the patients who have discontinued treatment.

Additional supportive summaries

Summary statistics will be given for the number of days from censoring to DCO for all censored patients, see [Section 3.2.2.1](#).

Additional summaries will be produced for the following points:

- The duration of follow-up will be summarised using median time from the treatment start date to the censoring date (date last known to have not progressed) in censored (not progressed) patients only.
- The number and percentage of patients who are censored due to two or more consecutive missed RECIST assessments.
- New lesions (ie, sites of new lesions).

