1.3 Number of Patients

It has been determined that approximately 150 patients are appropriate to characterize the frequency of tumour genetic and proteomic markers at disease progression regardless of their prevalence. [Table 2](#) displays the precision of the estimated frequency of mutation when, for example, 50 evaluable paired biopsies are available.

The final analysis will be performed at study end, and when approximately 50 patients have evaluable paired biopsies upon progression. Assuming a 70% of rate of patients having a biopsy at both baseline and progression, and with an assumed technical failure rate of 30% of the samples (assume an overall failure rate of 51%), then we should expect approximately 50 evaluable paired biopsies to be available when approximately 103 of the 150 patients have progressed, which would be expected to occur approximately 38 months after the first patient is enrolled. This calculation assumes patients are recruited over 12 months, exponentially distributed progression times with a 19-month median and a 2-piece recruitment function that assumes an exponentially distributed recruitment rate.

Table 2 Precision of Estimates of Marker Frequency with 50 Available and Evaluable Paired Biopsies

Marker Frequency	95% confidence interval ^a
10%	(3%, 22%)
30%	(18%, 45%)
50%	(36%, 64%)

^a Exact binomial confidence intervals.

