3.2.2.1 Progression-free survival

PFS is defined as the time from the first dose of osimertinib until the date of RECIST 1.1-defined progression or death (by any cause in the absence of progression) regardless of whether the patient withdraws from therapy or receives another anticancer therapy prior to progression. PFS is calculated in months as follows:

$$PFS = \frac{\text{date of objective disease progression or censoring} - \text{date of first dose of osimertinib} + 1}{30.4375}$$

Patients who have not progressed or died at the date of analysis will be censored at the time of the latest date of assessment from their last evaluable RECIST 1.1 assessment.

However, if the patient progresses or dies after two or more missed visits (126 days), the patient will be censored at the time of the latest evaluable RECIST 1.1 assessment.

Given the scheduled visit assessment scheme (i.e., eight-weekly for the first 3.5 years [D1277] then ten-weekly thereafter) the definition of 2 missed visits will change. Due to a delay in enacting CSP version 5.0 there was some variability in when patients transitioned to 10-weekly visit. However, we will apply the following rules to all patients.

1. If the previous RECIST 1.1 assessment is baseline, then two missing visits will equate to 17 weeks since the previous RECIST 1.1 assessment, allowing for a late visit (i.e., 2×8 weeks + 1 week for a late assessment = 17 weeks [119 days]).
2. If the previous RECIST 1.1 assessment is post baseline and \leq study day 1169, then two missing visits will equate to 18 weeks since the previous RECIST 1.1 assessment, allowing for early and late visits (i.e., 2×8 weeks + 1 week for an early assessment + 1 week for a late assessment = 18 weeks [126 days]).
3. If the previous RECIST 1.1 assessment study day is > 1169 and ≤ 1225 , then the two missed visits occur over the period when the scheduled frequency of RECIST 1.1 assessments changes from eight-weekly to ten-weekly, then this will equate to 21 weeks (i.e., take the average of 8 and 10 weeks which gives 9 weeks and then apply same rationale, hence 2×9 weeks + 1 week for an early assessment + 2 week for a late assessment = 21 weeks [147 days]).
4. If the previous RECIST 1.1 assessment study day is > 1225 (when the scheduling changes to ten-weekly assessments), two missing visits will equate to 24 weeks (i.e., 2×10 weeks + 2 week for an early assessment + 2 week for a late assessment = 24 weeks [168 days]).

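### PFS follow-up is to be reported as a median in censored patients only, which selects on the outcome and understates follow-up when there is dropout; reverse Kaplan-Meier avoids this

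*SAP*

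**What the plan says.** Among the supportive PFS summaries in SAP 4.2.9.2, duration of follow-up is the median time from treatment start to "the censoring date (date last known to have not progressed) in censored (not progressed) patients only". Neither document names reverse Kaplan-Meier or any other estimator of PFS follow-up.

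The censoring date comes from SAP 3.2.2.1. Patients without an event will "be censored at the time of the latest date of assessment from their last evaluable RECIST 1.1 assessment". In addition, "if the patient progresses or dies after two or more missed visits (126 days), the patient will be censored" at the last evaluable assessment. The length that counts as two missed visits is then varied by study day. Patients with no evaluable post-baseline visit or no baseline data are censored at Day 1, unless they die within two visits of baseline.

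SAP 4.2.9.2 plans two companion summaries. One is a gap to data cut-off: "Summary statistics will be given for the number of days from censoring to DCO for all censored patients". The other is the number and percentage of patients censored for two or more consecutive missed assessments. Time on study (SAP 4.2.8) and total safety follow-up (SAP 3.3.3) are separate quantities and do not measure PFS follow-up.

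**The concern.** Readers use median follow-up to judge how mature a PFS curve is. Restricting it to patients who have not progressed makes the denominator depend on the outcome. A patient who stays under observation for years will usually progress and drop out of the summary. A patient lost at month 3 without progression cannot leave it. As the data mature, the censored group shrinks and early losses become a larger share of it. This study is analysed late, when most patients should have progressed, so the pull downwards could be large. The reported figure could then suggest much shorter observation than the patients actually had.

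**Working it through.** **Inputs from the documents.** SAP 1.3 gives "exponentially distributed progression times with a 19-month median", and states that "approximately 103 of the 150 patients have progressed", which "would be expected to occur approximately 38 months after the first patient is enrolled". Protocol 8.1 gives the accrual: 100 patients in months 0–5, a 6-month pause, then 50 patients in 1 month (months 11–12). SAP 1.2 plans the final cut-off in Q2 2023.

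**Assumptions.**
- First patient in Q2 2018, a date found only in the protocol's version history. This puts the cut-off at about month 60. Month 38, the planning time in SAP 1.3, is shown as well.
- Dropout before progression is exponential and independent at 0, 0.3, 0.6 or 1.0% per month. The documents give no rate, so this is a range.
- Entry is uniform within each recruitment period.

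**Reproducing the plan's own figure.** The hazard is λ = ln 2 / 19 = 0.0365 per month. Expected progressions at month 38 are the sum over recruitment periods of n × [1 − mean of exp(−λ(38 − u))], where u is entry time:
- Months 0–5: 100 × (1 − 0.2743) = 72.6
- Months 11–12: 50 × (1 − 0.3803) = 31.0
- Total: 103.6, against about 103 stated. The model reproduces the plan.

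At month 60 the same formula gives 100 × (1 − 0.1229) + 50 × (1 − 0.1705) = 129.2 of 150 (86%). With no dropout, only 14% of patients would be in the censored group.

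**Mechanism by hand.** Take ten patients: dropouts at months 2 and 4, six progressions between months 6 and 30, and two ongoing at months 55 and 58.
- Censored-only median: the values are 2, 4, 55 and 58, so (4 + 55)/2 = 29.5 months.
- Reverse Kaplan-Meier: 9/10 × 8/9 = 0.80 after month 4. It is unchanged through the progressions, then 0.80 × 1/2 = 0.40 at month 55. The median is 55 months.

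**Size under the plan's model.** Large-sample simulation, medians in months. The censored-only values vary by up to about 1 month between runs.

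| Cut-off | Dropout per month | Lost before progression | Censored-only | Reverse Kaplan-Meier | Entry to cut-off |
|---|---|---|---|---|---|
| 60 | 0 | 0% | 55.7 | 56.2 | 56.2 |
| 60 | 0.3% | 7% | 49 | 56 | 56.2 |
| 60 | 0.6% | 13% | 39 | 49 | 56.2 |
| 60 | 1.0% | 20% | 22 | 49 | 56.2 |
| 38 | 0 | 0% | 33.7 | 34.2 | 34.2 |
| 38 | 0.3% | 5% | 28–29 | 34 | 34.2 |
| 38 | 0.6% | 10% | 27 | 33 | 34.2 |
| 38 | 1.0% | 17% | 26 | 29 | 34.2 |

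In the 1.0% row at month 60, dropouts make up about 71% of the censored group (19.8% of patients lost, out of 27.9% censored). In every row, reverse Kaplan-Meier agrees to about 0.1 months with the true median of min(dropout time, cut-off minus entry).

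A different dropout pattern, in simulated trials of 150 patients with cut-off at month 60, gives the same direction. With 10% of patients lost in months 0–6 the medians are 40.7 against 55.2; with 15% lost they are 19.3 against 54.3. In trials of that size with no dropout the average gap is 1.0 month (cut-off 38) to 1.4 months (cut-off 60).

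**The case against.** The strongest reply is that the SAP labels the statistic openly and surrounds it with summaries that would expose early censoring: days from censoring to cut-off, the count censored for missed assessments, and study discontinuations with reasons (SAP 4.2.1). That is true. A careful reader could see that something had pulled the median down, but could not recover the right figure from those lines. Declaring the restriction does not remove the selection.

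The size is also open to challenge, and this stands. The dropout rates are assumed. The protocol limits early loss by continuing RECIST assessments after treatment stops or another therapy starts (Protocol 4.3.2 and 5.1.1). The largest gap, about 26 months, needs roughly 20% of patients lost and a month-60 cut-off; at month 38 the same rate gives a gap of 2 to 3 months.

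Reverse Kaplan-Meier has limits too. A reader might infer that it returns the time from entry to cut-off. It does not. It estimates the median censoring time, so at 1.0% dropout and month 60 it gives 49 rather than 56.2 months, because observation really was shorter. Run on the same data, it also inherits the back-dating after two or more missed visits in SAP 3.2.2.1. That censoring depends on a later progression or death, so independence is doubtful there, and the simulation does not model it.

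**Conclusion.** The point holds as a reporting matter. The planned follow-up median selects on the outcome and understates PFS follow-up when there is dropout. Under the plan's accrual and PFS assumptions, the shortfall against reverse Kaplan-Meier at month 60 is about 7, 10 or 26 months for assumed dropout of 0.3, 0.6 or 1.0% per month. At month 38 it is about 5, 6 or 2–3 months. With no dropout it is about 0.5 months. These figures rest on the assumed dropout and, for month 60, on a first-patient date given only in the version history.

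Two wider readings are not supported. One is that the PFS results are biased: the Kaplan-Meier estimate, its interval, the primary endpoint and the sample size do not use this summary. The other is that it misstates the maturity of every time-to-event endpoint. It bears on PFS, and on DoR because SAP 3.2.2.3 takes over the PFS censoring time. TFST has its own censoring rule (SAP 3.2.2.6). In a single-arm exploratory study this is a minor improvement.

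**What to change.** In SAP 4.2.9.2, define median PFS follow-up as the reverse Kaplan-Meier median in the full analysis set: the same PFS times, with censoring counted as the event and progression or death as censored. State that it estimates observation time under the PFS censoring rules, including the missed-visit rule. If the censored-only median is kept, label it as describing patients without a PFS event. Keep the companion summaries as planned. The cost is one extra line of code on the existing PFS dataset and one row in a table; no new data are needed.

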4.2.9.3 Confirmed objective response rate

Objective response rate will be summarised as the proportion of patients with a response (ie, CR/PR indicating a response of CR/PR being recorded at 1 visit and confirmed by repeat imaging no less than 4 weeks later with no evidence of progression between the initial and CR/PR confirmation visit), along with the associated exact binomial 95% CI using the Clopper-Pearson method. Patients in the FAS must have evidence of disease at baseline to be included in the denominator.

4.2.9.4 Duration of response

Duration of response will be analysed using K-M methodology from which the median and 95% CI will be produced with event rates at clinically important landmarks as explained in [Section 4.2.9.2](#). Only patients who have responded (a confirmed response) will be included in the analysis.

4.2.9.5 Disease control rate

Disease control rate will be summarised as the proportion of patients with disease control (ie, an overall response of PR/CR or SD at ≥ 8 weeks), along with the associated exact binomial 95% CI using the Clopper-Pearson method. Patients in the FAS must have evidence of disease at baseline to be included in the denominator.

4.2.9.6 Time to treatment discontinuation or death (TTD)

TTD will be analysed using K-M methodology from which the median and 95% CI will be produced with event rates at clinically important landmarks as explained in [Section 4.2.9.2](#).

4.2.9.7 Time to first subsequent therapy or death (TFST)

TFST will be analysed using K-M methodology from which the median and 95% CI will be produced with event rates at clinically important landmarks as explained in [Section 4.2.9.2](#).

4.2.10 Safety

The following sections describe the planned safety summaries for AEs, SAEs, deaths, laboratory parameters, vital signs, physical examinations and ECGs.

4.2.10.1 Adverse events

Only TEAEs, ie, AEs developing or worsening in severity (from baseline severity) on or after the first day of osimertinib administration up to and including 28 days after the last dose of osimertinib (defined as the treatment period) will be summarised.

Any AE occurring before the first dose of osimertinib and AEs occurring 28 days after last dose will be listed only and not included in the summaries.

Any AEs that occur after a patient has received further therapy for cancer (following discontinuation of osimertinib) will be flagged in the data listings. Any AEs that occur after a patient has received further therapy for cancer within 28 days after discontinuing osimertinib are included in the summaries.

The number of patients experiencing each AE will be summarised by the MedDRA system organ class, MedDRA preferred term and worst CTCAE grade. The number and percentage of patients with AEs in different categories (ie, causally related, maximum reported intensity, CTCAE grade ≥ 3) will be summarised, and events in each category will be further summarised by MedDRA system organ class and preferred term. Events will be displayed by international SOC order and alphabetical PT. Subjects who report the same AE several times will only appear once in that row.

SAEs and deaths will be summarised.

4.2.10.2 Laboratory evaluations

Laboratory data obtained up until treatment discontinuation will be included in the summary tables. Absolute values and change from baseline for all continuous haematology, clinical chemistry and urinalysis laboratory parameters will be summarised for each visit.

Shift tables for change in grade from baseline by treatment group will be produced. The laboratory parameters for which CTC grade shift outputs will be produced are:

- Haematology: basophils, eosinophils, haemoglobin, B-leukocyte differential count (absolute count), lymphocytes, monocytes, neutrophils and platelets.
- Clinical chemistry: alanine aminotransferase (ALT), albumin, alkaline phosphatase, aspartate aminotransferase (AST), bilirubin (total), calcium, creatinine, potassium, and sodium.
- Urinalysis: erythrocytes, glucose and protein.

Hy's law

The following summaries will include the number (%) of patients who have:

- Elevated ALT, AST, and total bilirubin during the study
- AST or ALT $\geq 3 \times$ ULN and total bilirubin $\geq 2 \times$ ULN during the study (potential Hy's law): the onset date of ALT or AST elevation should be prior to or on the same date of total bilirubin elevation.

Liver biochemistry test results over time for patients with elevated ALT or AST (ie, $\geq 3 \times$ ULN) and elevated total bilirubin (ie, $\geq 2 \times$ ULN) at any time will be plotted.

Individual patient data where ALT or AST plus total bilirubin are elevated at any time will be listed (ie, ALT and/or AST $\geq 3 \times$ ULN and total bilirubin $\geq 2 \times$ ULN, at any time).

4.2.10.3 Vital signs

Vital sign data obtained up until the 28-day safety follow-up visit will be included in the summary tables and will be summarised using descriptive statistics (mean, median, standard deviation, minimum, maximum and number of patients). As detailed in [Section 3.3.6](#), changes from baseline will also be summarised.

4.2.10.4 Electrocardiograms

ECG data obtained up until the 28-day safety follow-up visit will be included in the summary tables. The following parameters will be summarised by visit:

- QTc Interval Fredericia > 470 ms (Yes, No)
- Overall Evaluation (Normal, Abnormal)
- Clinical significance (Yes, No)

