5.2.2 Physical examination

A physical examination will be performed and include an assessment of the following: general appearance, skin, head and neck (including ears, eyes, nose, and throat), respiratory, cardiovascular, abdomen, lymph nodes, thyroid, musculoskeletal (including spine and extremities), and neurological systems.

5.2.3 *Electrocardiogram*

5.2.3.1 *Resting 12-lead electrocardiogram*

Twelve-lead ECG will be performed at the visits indicated in the Study Plan.

Twelve-lead ECGs will be obtained after the patient has been resting semi-supine for at least 10 minutes prior to times indicated. All ECGs should be recorded with the patient in the same physical position. For each time point one ECG recording should be taken. A standardised ECG machine should be used and the patient should be examined using the same machine throughout the study if possible.

After the paper ECG has been recorded, the Investigator or designated physician will review the ECG and may refer to a local cardiologist if appropriate. A copy of the ECG should be filed in the patient's medical records. If an abnormal ECG finding at screening or baseline is considered to be clinically significant by the Investigator, it should be reported as a concurrent condition. For all ECGs, details of rhythm, ECG intervals and an overall evaluation will be recorded.

If there is a clinically significant abnormal ECG finding during the treatment period, this should be recorded on the AE eCRF, according to standard AE collection and reporting processes. A 28-day follow-up assessment will be required if an on-treatment assessment was abnormal at the time of discontinuation of study therapy, to confirm reversibility of the abnormality.

5.2.4 *Echocardiogram/Multigated acquisition scan*

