3.3.1 General considerations for safety assessments

Time windows will need defining for any presentations that summarise values by visit ([Table 7](#)). The following conventions should also apply:

- The time windows should be exhaustive so that data recorded at any time point has the potential to be summarised. Inclusion within the time window should be based on the actual date and not the intended date of the visit.
- All unscheduled visit data should have the potential to be included in the summaries.
- The window for the visits following baseline will be constructed in such a way that the upper limit of the interval falls halfway between the two visits (the lower limit of the first post-baseline visit will be Day 2). If an even number of days exists between two consecutive visits, then the upper limit will be taken as the midpoint value minus one day.
- For summaries showing the maximum or minimum values, the maximum/minimum value recorded on treatment will be used (regardless of where it falls in an interval).
- Listings should display all values contributing to a time point for a patient.
- For visit-based summaries, if there is more than one value per patient within a time window then the value closest to the planned study day should be summarised, or the earlier in the event the values are equidistant from the planned study day. The listings should highlight the value for that patient that went into the summary table, wherever feasible.
- For summaries at a patient level, all values should be included, regardless of whether they appear in a corresponding visit-based summary, when deriving a patient level statistic such as a maximum.
- Baseline will be defined as the last non-missing measurement prior to dosing with study treatment. Where safety data are summarised over time, study day will be calculated in relation to date of first study treatment. For safety endpoints the last observation before the first dose of IP will be considered the baseline measurement unless otherwise specified. Assessments on the day of the first dose where neither time nor a nominal pre-dose indicator are captured will be considered prior to the first dose if such procedures are required by the protocol to be conducted before the first dose.

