3.3.6 Vital signs

Vital signs data (blood pressure, pulse and temperature) will be obtained at every visit up until treatment discontinuation and will be used for reporting. Change from baseline in vital signs variables will be calculated for each post-dose visit on treatment. For derivation of post-baseline

visit values, considering visit window, and to handle multiple records, derivation rules as described in [Section 3.3.1](#) will be used.

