3.3.8 Electrocardiograms

Electrocardiogram (ECG) data (details of rhythm, ECG intervals and an overall evaluation) will be obtained at every visit until treatment discontinuation. If there is an abnormal on-treatment assessment at the time of treatment discontinuation then a 28-day follow-up assessment will be required to confirm reversibility of the abnormality.

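### SAP 4.2.10.4 admits 28-day follow-up ECGs to the by-visit tables, but Table 7 has no off-drug row, so they can be tabulated as ordinary Week-n results

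*SAP*

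**What the plan says.** SAP 4.2.10.4 sets the data cut for the ECG tables: "ECG data obtained up until the 28-day safety follow-up visit will be included in the summary tables". It then says "The following parameters will be summarised by visit" and names three: QTcF above 470 ms, overall evaluation, and clinical significance. The SAP plans no other ECG summary.

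No routine ECG is scheduled at 28 days. SAP 3.3.8 creates one for a selected group: "If there is an abnormal on-treatment assessment at the time of treatment discontinuation then a 28-day follow-up assessment will be required", to see whether the abnormality reverses. Protocol 5.2.3.1 has the same rule: "A 28-day follow-up assessment will be required if an on-treatment assessment was abnormal at the time of discontinuation of study therapy".

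SAP 3.3.1 makes the visit windows exhaustive and places each value by its actual date. If a patient has more than one value in a window, "then the value closest to the planned study day should be summarised", and ties go to the earlier value. The only on-treatment restriction in 3.3.1 covers maximum and minimum summaries, and none is planned for ECG. Table 7 lists Screening, Day 1 and Week-n rows up to Day 2387. It has no row for discontinuation or follow-up.

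SAP 4.2.10.2 cuts the laboratory tables at treatment discontinuation. For vital signs, 4.2.10.3 says "Vital sign data obtained up until the 28-day safety follow-up visit will be included in the summary tables", while 3.3.6 says "Change from baseline in vital signs variables will be calculated for each post-dose visit on treatment".

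**The concern.** Read together, these rules send an off-drug ECG into a row that otherwise holds scheduled treatment-period visits. The patients who contribute such ECGs are mainly those whose last on-drug ECG was abnormal, so they are not a random sample of those who stop. Two things can follow. The off-drug ECG can be counted under a later Week n, when the patient was no longer taking osimertinib. Or it can share a window with the discontinuation ECG, and the nearest-to-target rule can tabulate it in place of the on-drug tracing. In both cases the only planned ECG summary reports, under a treatment-visit label, a value that does not describe a patient on treatment. QTc prolongation is a listed adverse drug reaction with its own dose-adjustment rules (Protocol 1.1 and Table 4), so the ECG table should be readable as on-drug data.

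**Working it through.** **Inputs.** Window limits and target days come from SAP Table 7. The selection rule is in SAP 3.3.1. The follow-up is timed at 28 days (+7) after the last dose (Protocol 4.3.1), so the base case is a gap of 28 to 35 days between the two ECGs.

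**Reproducing Table 7.** SAP 3.3.1 puts the upper limit at the midpoint between visits, less one day when the gap is even. Between D225 and D281 the midpoint is 253, giving D252. Between D1233 and D1303 it is 1268, giving D1267. All 42 upper limits for Visits 3 to 44 match; Visit 45 has no later visit, so D2387 is taken as printed. With target T, the 56-day windows (Visits 11 to 28) run from T−28 to T+27, and the 70-day windows (Visit 30 on) from T−35 to T+34.

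**Effect 1: tabulated under a later Week n.** Take a stop-day ECG on the target day T.
- 56-day windows: the follow-up falls on T+28 to T+35. The window ends at T+27, so it always lands in the next row. Example: a stop on D449 (Week 64) gives a follow-up on D477 to D484, inside D477-D532, shown as Week 72.
- 70-day windows: T+28 to T+34 stays in the same window and the stop-day value is kept, being on target. T+35 lands in the next row.
- Visits 3 to 9: these windows are at most 28 days long, so a follow-up 28 or more days later always lands in a later row, whatever the stop day.

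**Effect 2: replacement in the same row.** Let the stop-day ECG be *a* days before target and the gap be *g*. The off-drug value is nearer when |g − a| < a, that is, when a > g/2.
- g = 28: a > 14, so 15 days or more before target.
- g = 35: a > 17.5, so 18 days or more before target.
- In Visits 3 to 10 the lower limit is never more than 14 days before target (for example D155 against D169), so replacement is impossible. It first becomes possible at D197.

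Stop days within a window that give each result:

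| Window | Gap | Replaced | Stop-day value kept | Next row |
|---|---|---|---|---|
| 56-day | 28 | 14 | 14 | 28 |
| 56-day | 35 | 11 | 10 | 35 |
| 70-day | 28 | 21 | 21 | 28 |
| 70-day | 35 | 18 | 17 | 35 |

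Example of replacement: abnormal stop-day ECG on D424, normal follow-up on D452, both in D421-D476 with target D449. The distances are 25 and 3 days, so Week 64 shows the normal off-drug ECG.

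**Check against the visit schedule.** Scheduled visits are allowed ±7 days in 8-week cycles and ±14 days in 10-week cycles. A stop-day ECG at most 7 days early cannot meet a > 14. At 14 days early with a 28-day gap, the two values tie and the earlier, on-drug one is kept. Within those windows, replacement is zero at gaps of 28 to 35 days.

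**Range.** The discontinuation visit has its own ±7 day window, so the gap could run from 21 to 42 days. At 42 days replacement falls to 7 of 56 and 14 of 70 stop days. At 21 days it rises to 18 of 56 and 25 of 70. The threshold then drops to 11 days before target, and replacement also becomes possible on 4 of 28 days in the Visit 6 to 9 windows and 4 of 42 in Visit 10.

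**The case against.** The cut-off may be deliberate. For adverse events, SAP 4.2.10.1 defines the treatment period as running to 28 days after the last dose, and Table 7 prints only Week n, not on-treatment. That is fair as an account of the data cut. It does not justify the label: SAP 3.3.8 itself separates the on-treatment ECG from the follow-up done to test reversibility, and with the +7 day allowance the follow-up can fall after the 28 days.

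A reader might infer from the table of stop days that 20% to 30% of these patients would have an on-drug abnormality overwritten (11/56 to 21/70). The documents do not support that. Those shares treat every stop day in a window as equally likely, whereas scans and visits run on 8- or 10-week schedules and stops may well cluster at them. Replacement also changes the tabulated category only if the follow-up result differs.

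A reader might also infer that the abnormality is lost from the report. It is not. Under SAP 3.3.1 the listings show all values contributing to a time point and highlight the one tabulated where feasible. Clinically significant on-treatment findings are recorded as AEs (Protocol 5.2.3.1), with stop date and outcome (Protocol 6.3.3), and summarised (SAP 4.2.10.1).

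Nor do vital signs carry the same problem. None are scheduled at 28 days, 3.3.6 says they are obtained up to discontinuation, and 4.2.10.3 refers back to 3.3.6 for change from baseline. Only the cut-off wording is out of line.

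Finally, the separate table shells (SAP 4.1) could add a follow-up row. Neither document says they do.

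**Conclusion.** The point stands as a minor defect in a stated rule. As written, an off-drug ECG, required only after an abnormal ECG at discontinuation, is eligible for an ordinary Week-n row. The usual consequence is a count under a later visit. Replacement of the on-drug ECG is the exception: at gaps of 28 to 35 days it needs a stop-day ECG from Day 197 on, more than 14 to 17 days before target.

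This rests on reading the cut-off as including the follow-up visit, on the 28 to 35 day gap, and on distance from the Table 7 target day. SAP 3.2.2.1 notes that patients moved to 10-weekly visits at varying times, so after 3.5 years a patient's own schedule may not match those targets. The number of patients affected cannot be computed from the documents. The ECG tables are descriptive, in a single-arm profiling study, and the primary and efficacy endpoints do not use them.

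**What to change.** In SAP 4.2.10.4, limit the by-visit ECG tables to data up to and including the treatment discontinuation visit, as 4.2.10.2 does for laboratory data. Show 28-day follow-up ECGs in a separate follow-up row outside the Table 7 windows. Both mislabelling and replacement then fall to zero in every window. Align the cut-off wording in 4.2.10.3 with 3.3.6 for consistency. Cross-tabulating the follow-up ECG against the same patient's discontinuation ECG would show reversibility directly, but is optional. The cost is an edit to two SAP sections, one programming flag and one extra table row, with no new data.
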